#### **2.3.2 Secondary endpoints:**

-To measure the difference in serum levels of 24S-hydroxycholesterol (24OHC) , osteopontin and matrix metalloproteinases (and also MMPI's) between baseline and after fingolimod treatment at month 12 and month 24.

-To evaluate the effect of fingolimod on cognitive performance in highly active relapsing remitting multiple sclerosis patients comparing baseline, month 12 and month 24, as assessed by PASAT and Stroop test.

-To evaluate the effect of fingolimod on brain gray matter atrophy and thalamic atrophy by comparing MRI data between baseline and month 24.

-To evaluate the correlation between effect of fingolimod on cognitive performances and brain atrophy (gray matter atrophy and thalamic atrophy) by comparing baseline and month 24.

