### **6.4.2 Magnetic Resonance Imaging (MRI) Assessments**

MRI scans will be obtained at baseline and at months 6, 12, 18 and 24 by using 1.5T MRI for measuring gray matter atrophy and thalamic atrophy.

A standard scanning protocol will be used for MRI in all centers.

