#### **9.4.3.1 Data analysis**

##### **General Approach**

All Statistical analyses will be performed with MedCalc Statistical Software version 13.1.2 (MedCalc Software bvba, Ostend, Belgium; <http://www.medcalc.org>; 2014) at the 5% significance level using 2-sided tests or 2-sided Confidence Intervals.

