##### Comparisons of Two Groups

Student t test will be used for comparisons of two independent normally distributed groups, Mann Whitney u test will be used for comparisons of two independent non-normally distributed groups.

Paired samples t test will be used for comparisons of two dependent normally distributed groups, Wilcoxon Signed Rank test will be used for comparisons of two independent normally distributed groups.

For comparisons of categorical and independent data Chi-Square test or Fisher Exact test (where appropriate) will be used.

To assess categorical and dependent variables Mc Nemar test will be used.

Normality of continuous data will be tested by using Shapiro-Wilk test.

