#### **9.4.3.2 Statistical Methods by Evaluation of Study Objective**

##### **Primary Objective:**

Primary objective of the study will be evaluated by the statistical methods which are stated below:

- Calculated scores of BICAMS (SDMT, CVLT2 and BVMTR) at baseline, 12th month and 24th month will be compared by using Repeated Measures ANOVA (if variables are non-normally distributed Friedman Test).

Post-Hoc comparisons will be done with Tukey test. (if Friedman test was used, Wilcoxon Signed Rank test will be used for Post-Hoc comparisons.)

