##### **Secondary Objectives:**

Secondary objectives of the study will be evaluated by the statistical methods which are stated below:

- The effect of fingolimod on biomarkers (24OHC, Osteopontin and Metalloproteinase) at months 6, 12, 24 will be evaluated by comparing the levels of biomarkers. The evaluation among time points will be made by using Repeated Measures ANOVA.
- The effect of fingolimod on brain gray matter atrophy and thalamic atrophy will be evaluated by comparing MRI parameters at baseline, 6th, 12th, 24th months.

The comparison among time points will be made by Repeated Measures ANOVA. (if variables are non-normally distributed Friedman Test).

- Investigation the effect of fingolimod on cognitive performance in highly active relapsing remitting multiple sclerosis patients comparing baseline, 12th and 24th month, as assessed by PASAT and Stroop test will be made by Repeated Measures ANOVA. (if variables are non-normally distributed Friedman Test).
- Correlation between cognitive performance and MRI data will be calculated by using Pearson Correlation Coefficient (or Spearman Correlation Coefficient) between PASAT, STROOP and BICAMS tests scores and MRI parameters.

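### The MRI atrophy endpoint is baseline versus Month 24, but its assigned test is an omnibus comparison over four visits with no baseline-to-Month-24 contrast or confidence interval pre-specified

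*Combined protocol and SAP*

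**What the plan says.** Section 2.3.2 lists as a secondary endpoint the effect of fingolimod on "brain gray matter atrophy and thalamic atrophy by comparing MRI data between baseline and month 24". That is one comparison of two time points. The correlation endpoint in the same section also runs from baseline to Month 24.

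Under its Secondary Objectives, section 9.4.3.2 assigns the analysis. The effect on "brain gray matter atrophy and thalamic atrophy will be evaluated by comparing MRI parameters at baseline", 6, 12 and 24 months, and "The comparison among time points will be made by Repeated Measures ANOVA", with Friedman's test if the data are non-normal. Nothing further is specified for MRI.

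Other parts of the plan that bear on this:

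- Section 9.4.3.2, Primary Objective: "Post-Hoc comparisons will be done with Tukey test", or Wilcoxon signed rank after Friedman. This stands under the BICAMS analysis only.
- Section 9.4.3.1, Comparisons of Two Groups: "Paired samples t test will be used for comparisons of two dependent normally distributed groups". No endpoint is attached to it.
- Section 9.4.3.1, Comparisons of Several Groups: the Tukey HSD rule follows the sentence on independent groups. The sentences on dependent groups name no follow-up test.
- Section 9.4.3.1, Descriptive Statistics: quantitative variables get a mean, SD and two-sided 95% CI of the mean.
- Section 9.4.4: no supportive analyses are planned.
- Section 6.4.2: "MRI scans will be obtained at baseline and at months 6, 12, 18 and 24". The Month 18 scan is in neither the endpoint nor the assigned test.

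**The concern.** The null hypothesis of the four-visit ANOVA is that all four visit means are equal. The endpoint asks whether the Month 24 mean differs from the baseline mean. Rejecting the first does not answer the second, because a change confined to the middle visits is enough to reject it. Followed literally, the plan could report a significant atrophy result when there was no net 24-month change.

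The study has one arm, so the size of the 24-month change and its uncertainty are the main interpretable MRI result. The plan does not ask for that interval. With no comparison named in advance, the choice of which visits to compare after a significant omnibus test is also left open until the data are seen.

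**Working it through.** **The plan's own figures.** The plan gives none for MRI. Section 9.6 sizes the study on SDMT, without power, at 73 patients, raised to 80 for 10% loss to follow-up. The 73 matches a single-proportion precision formula that the plan does not name: 1.96² × 0.05 × 0.95 / 0.05² = 72.99, so 73. This says nothing about MRI. I use 73 only as the evaluable number.

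**Inputs.** From the documents: n = 73 (section 9.6), and testing "at the 5% significance level using 2-sided tests or 2-sided Confidence Intervals" (section 9.4.3.1). Assumed, because the documents are silent: a standardised Month 24 mean change (mean over SD of the change) of 0.3324, chosen so that a paired t test of baseline versus Month 24 has 80% power at n = 73. Also assumed at first: equal variance and equal correlation across visits.

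**Formulas.**

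- Contrast: noncentral t with 72 df and noncentrality 0.3324 × √73 = 2.84. Power is 80% by construction.
- Omnibus: noncentral F with 3 and 3 × 72 = 216 df. Scale the SD of a between-visit difference to 1. The error variance is then 1/2 and λ = 2 × n × d² × SS, where SS is the sum of squared deviations of the visit pattern from its mean. Here 2 × 73 × 0.3324² = 16.13.

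**Results under equal correlation.** Each pattern is the mean change at months 0, 6, 12 and 24, as a fraction of the assumed shift.

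| Pattern | Values | SS | λ = 16.13 × SS | Omnibus power |
|---|---|---|---|---|
| Linear | 0, 0.25, 0.5, 1 | 0.547 | 8.8 | 69% |
| Decelerating | 0, 0.45, 0.7, 1 | 0.537 | 8.7 | 68% |
| Months 6 and 12 both halfway (least favourable) | 0, 0.5, 0.5, 1 | 0.500 | 8.1 | 65% |
| Early drop, then plateau | 0, 1, 1, 1 | 0.750 | 12.1 | 84% |
| Change at Month 24 only | 0, 0, 0, 1 | 0.750 | 12.1 | 84% |
| **Month 6 only, no Month 24 change** | 0, 1, 0, 0 | 0.750 | 12.1 | **84%** |
| **Months 6 and 12 only, no Month 24 change** | 0, 1, 1, 0 | 1.000 | 16.1 | **93%** |

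The last two rows show the mismatch: the omnibus is very likely to be significant although the endpoint quantity is exactly zero. If the contrast is set at 90% power instead, linear change gives the omnibus 83%.

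**Relaxing equal correlation.** Patients may lose volume at different rates. I simulated linear mean change at n = 73, with 8,000 runs per scenario and 30%, 60% or 90% of the variance of the Month 24 change due to patient slopes. Omnibus power was 75%, 79% and 80% with Greenhouse-Geisser correction. Without correction it was 76%, 82% and 87%, but at the highest share the uncorrected type I error was 8.7%, so the corrected figures are the fair comparison. For an early plateau, the corrected power rose to 90%, 95% and 99%.

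**The case against.** The plan contains the pieces of an answer. It lists a paired t test for two dependent groups, which is the form of the section 2.3.2 endpoint. Its descriptive statistics would report each visit mean with a 95% CI, so a reader could subtract the baseline mean from the Month 24 mean and would notice a mid-study shift that had reversed. The endpoint is secondary, in a single-arm open-label study that makes no power claim for MRI.

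This disposes of three stronger readings:

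- A reader might infer that the endpoint is never tested directly. The documents support only that no direct test is assigned to it, since the paired t test is available as a general method.
- A reader might infer that no estimate or CI would be reported. Visit means and their intervals are planned. What is missing is an interval for the change. It cannot be derived from the separate visit intervals without the within-patient correlation.
- A reader might infer that the omnibus test loses power. The documents give no MRI effect, SD or correlation, and the direction depends on the time course and the covariance. A drop from 80% to 69% needs linear loss and equal correlation together.

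The general listing does not cure the mismatch. Section 9.4.3.2 says that the secondary objectives are evaluated by the methods it lists, and for MRI that is the omnibus test alone. The authors wrote a post hoc step for BICAMS and none for MRI.

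**Conclusion.** The mismatch between endpoint and analysis is established from the text alone and needs no assumption. Section 2.3.2 asks a two-visit question, section 9.4.3.2 assigns a four-visit omnibus test, and no contrast, post hoc test or interval for the 24-month change is pre-specified.

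Its size is illustrative. At n = 73, with equal correlation and a shift that would give the contrast 80% power, a change limited to Month 6, or to Months 6 and 12, would give a significant omnibus result about 84% or 93% of the time with no net change at Month 24.

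Power is a secondary and conditional matter. Against 80% for the contrast, the omnibus ranges from about 65% to 84% across the equal-correlation patterns that end in a Month 24 change. It is about 75–80% for linear change with varying slopes, and higher still for an early plateau with varying slopes. A general loss of power is not shown. This is worth correcting as a secondary-endpoint issue. It does not affect the sample size or the primary analysis.

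**What to change.** In section 9.4.3.2, name the Month 24 minus baseline change (or percent change, stating which) with its two-sided 95% CI as the test of gray matter and thalamic atrophy. Obtain it by paired t test or Wilcoxon signed rank test, or as that contrast from a longitudinal model. If a model is used, list the visits in it and say whether the Month 18 scan enters. Keep the comparison across visits as supportive and amend section 9.4.4 to match.

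The cost is one or two sentences, with no new data and no change in sample size. The downside is that the omnibus result, and other shapes of change over time, become supportive rather than the main test.

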### **Stroop Test:**

The Stroop Color and Word Test assesses cognitive processing and provides valuable diagnostic information on brain dysfunction, cognition, and psychopathology. It is based on the observation that individuals can read words much faster than they can identify and name colors. It is a five minute test is applicable for those between the ages of 15 and 90.

This test was adapted from the paper-based Stroop Color-Word Interference Test (Golden, 1978) and consists of three 60-s trials, each of which was preceded by a set of eight practice items to insure the participant understood the task to follow. In the first trial (word reading, W), participants will read color words (RED, BLUE, YELLOW, GREEN) printed in black letters; in the second trial (color naming, C), they will name the colors used to print a row of four Xs; and in the third trial (color-word naming, CW), they will name the color of the print for a set of incongruent Stroop stimuli (e.g., BLUE printed with red letters). In each trial, the stimulus item appeared on the paper, the participant will respond verbally to the item, and either the experimenter (E-press condition) immediately will show the next item. The number of items completed in the allotted time will be recorded. In addition to the W, C, and CW scores, the combined score for word-reading and color-naming (W + C) might be examined as a particularly good measure of processing speed. Also, a measure of relative interference (RI) will be computed by dividing the difference between the color-naming and the color-word naming scores by the color-naming score ( $RI = \frac{C - CW}{C}$ ).

Stroop test will be performed to RRMS patients at baseline and at months 6, 12 and 24.

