#### **9.4.2 Secondary efficacy endpoints:**

The metric for the PASAT assessment is the number of correct answers.

The Stroop test yields three scores based on the number of items completed on each of the three stimulus sheets.

All MRI analysis will be performed at the Kocaeli University Faculty of Medicine which is the center of the study coordinator investigator.

SIENAX—cross-sectional method will be used to measure atrophy. (25)

Whole brain volume, total gray matter volume, cortical gray matter volume and deep gray matter volume will be measured.

White matter lesions will be segmented by using  $k$  nearest neighbor classification with tissue-type priors, The resulting lesion volume will be normalized for head size to create normalized lesion volume (26,27) Lesion filling will be applied to minimize the effect of hypointense lesions on atrophy measurements (28). Normalized whole-brain volume, normalized gray

matter volume (NGMV), and normalized white matter volume (NWMV) will be measured with SIENAX (part of FSL [Functional MRI of the Brain, or FMRIB, Software Library] 5.0.2, <http://www.fmrib.ox.ac.uk/fsl>) by using optimized parameters for brain extraction (29,30).

Deep gray matter volumes will be measured by using FSL FIRST software (31). Cortical thickness will be measured by using FreeSurfer 5.1 software (<https://surfer.nmr.mgh.harvard.edu/>) (32,33). FreeSurfer uses the T1-weighted image to locate the white matter and pial surface. The distance between both surfaces gives the cortical thickness at each location.

Thalamic and intracranial volumes will be segmented automatically. Thalamic volumes and thalamic fractions will be calculated as ratios of the left and right thalamic volume to the intracranial volume.

Correlation between effect of fingolimod on cognitive performances and brain atrophy will be explored.

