### **9.4.3 Statistical model, hypothesis, and method of analysis**

The basic hypothesis of the study is improvements in cognitive tests in RRMS patients. The sample size calculation for the study has been based on an improvement with treatment in a cognitive test (SDMT).

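### The PASAT/Stroop secondary endpoint is tested score by score with an omnibus test and names no lead Stroop score or Month 24 contrast, so a significant result would not show improvement

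*Combined protocol and SAP*

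**What the plan says.** Section 2.3.2 of the combined protocol and SAP lists one secondary endpoint for these tests, "comparing baseline, month 12 and month 24, as assessed by PASAT and Stroop test". Section 9.4.3.2 (Secondary Objectives) gives its analysis: "as assessed by PASAT and Stroop test will be made by Repeated Measures ANOVA", with Friedman's test for non-normal data. Section 9.4.3.1 (General Approach) sets all analyses "at the 5% significance level using 2-sided tests or 2-sided Confidence Intervals".

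Section 9.4.2 defines the scores: "The metric for the PASAT assessment is the number of correct answers", and "The Stroop test yields three scores based on the number of items completed on each of the three stimulus sheets". These are word reading (W), colour naming (C) and colour-word naming (CW). None is ranked above the others.

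The Stroop description in section 6.4.1 adds two derived scores. One is definite: "Also, a measure of relative interference (RI) will be computed by dividing the difference between the color-naming and the color-word naming scores". The other is optional: "the combined score for word-reading and color-naming (W + C) might be examined as a particularly good measure of processing speed".

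Section 9.4.3 states the hypothesis broadly: "The basic hypothesis of the study is improvements in cognitive tests in RRMS patients".

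Section 9.4.3.2 names post-hoc comparisons under the primary objective, but the PASAT/Stroop bullet has none. In the general section, post-hoc tests are attached to independent groups only. A paired t test is listed there in general terms and is not tied to PASAT, Stroop or Month 24.

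**The concern.** The endpoint reads as one question, but the plan answers it with four or more separate tests and does not say which one governs. Three problems follow.

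- **No direction.** A test over three visits can be significant because of a decline, or because of a Month 12 fluctuation that has gone by Month 24. Neither is the hypothesised improvement.
- **Several chances.** The hypothesis speaks of cognitive tests in general, so any one significant score could be offered in its support.
- **Choice of Stroop score.** The scores need not agree, and the plan leaves open which one is read.

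What is at stake is how the PASAT/Stroop result is interpreted. The sample size and the primary analysis are not affected.

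**Working it through.** The plan states no error rate for this endpoint, so there is no figure to reproduce.

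**1. Number of scores.** Section 9.4.2 gives PASAT (1) plus W, C and CW (3), so four. Section 6.4.1 adds RI (five) and optionally W+C (six). No passage assigns RI or W+C to the repeated-measures test, so four is the firm count and six the upper bound.

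**2. Bound under independence.** The chance of at least one p < 0.05 under the null is 1 − 0.95^k. For k = 4 this is 18.5%; for k = 6 it is 26.5%. The second figure overstates the rate, because RI and W+C are built from W, C and CW.

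**3. Simulation under the null.** n = 73 (section 9.6), three visits, repeated-measures ANOVA per score, RI and W+C derived. The documents give no SDs or correlations for these tests, so all are assumed. Set A, as mean/between-patient SD/within-patient SD: PASAT 45/8/4, W 95/14/7, C 70/11/5.5, CW 40/8/4, with 10,000 trials per correlation. For RI, lower counts as better.

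| Correlation among scores | Any significant, 4 scores | Any significant, 6 scores | Significant and Month 24 better, 4 scores | Significant and Month 24 better, 6 scores |
|---|---|---|---|---|
| 0 | 18.6% | 22.4% | 9.9% | 12.7% |
| 0.5 | 15.3% | 19.0% | 7.8% | 10.2% |
| 0.8 | 12.2% | 15.7% | 6.3% | 8.1% |

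Set B uses larger total SDs (W 16, C 12, CW 10, PASAT 10), a within-patient correlation of 0.75 and Stroop correlations from 0 to 0.9. It gives 18.1% down to 11.1% for four scores and 21.8% down to 13.9% for six. For six scores, a significant result that also favours Month 24 occurs in 12.2% down to 7.3%. Using n = 80 instead of 73 changes the six-score rate from 20.0% to 19.9% at a Stroop correlation of 0.5.

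The comparator for the last two columns of the table is one pre-named two-sided 5% contrast, which gives a false favourable result in 2.5% of trials.

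**4. Conflict between Stroop scores.** RI = (C − CW)/C = 1 − CW/C, so RI rises (more interference) whenever C improves proportionally more than CW. With illustrative scores C 70 to 77 and CW 40 to 42, both components improve, but RI goes from 30/70 = 0.429 to 35/77 = 0.455. The scores are invented; the property follows from the protocol's formula.

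**5. Does a Month 24 contrast lose power?** Suppose the change d is linear and the within-patient SD is σ. The omnibus noncentrality is n[(d/2)² + 0 + (d/2)²]/σ² = nd²/(2σ²). The baseline-to-Month 24 contrast has the same value, nd²/(2σ²), but spends one degree of freedom instead of two. At a noncentrality of 9.2 and n = 73, power is about 85% for the contrast and 77% for the omnibus test.

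**The case against.** The strongest reply is that no formal claim rests on this endpoint. It is a secondary endpoint in a single-arm, open-label Phase IV study that was sized without considering power and has no secondary success rule. Descriptive means with 95% CIs are already planned, so the direction at each visit will be visible. This stands in part. Formal error control over such scores is a trade-off, and its absence is not a fault in itself. But a CI for each visit mean is not a CI for the within-patient change, and the plan still chooses to test.

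A reader might infer that chance alone yields a cognitive effect in about one trial in five, or that the error rate is four times nominal. The documents do not support that as the general figure. It needs RI or W+C, which appear only in the test description, and it counts every significant omnibus result, including declines. On the four scores of section 9.4.2, and requiring Month 24 to be better, the rate is about half that or less.

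A reader might also infer that the Stroop scores contradict one another generally. The conflict shown involves RI only. RI measures relative interference and can differ from CW by definition.

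**Conclusion.** The point holds as a matter of specification. The plan names no lead Stroop score and no Month 24 contrast, so its omnibus tests cannot by themselves show the hypothesised improvement.

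The inflation is moderate. At least one significant result arises under the null in about 11% to 19% of trials for four scores, and up to about 22% for six. One that also favours Month 24 arises in about 6% to 10%, and up to about 13% for six, against 2.5% for a single contrast. These ranges rest on assumed SDs and correlations and on repeated-measures ANOVA; the higher ends belong to uncorrelated scores. The missing direction and contrast do not depend on those assumptions. The possible RI conflict follows from its formula and matters only if RI is used to read the Stroop result.

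**What to change.** In sections 2.3.2 and 9.4.3.2, define the secondary comparisons as the mean within-patient change from baseline to Month 24, with a 95% CI, for two scores: PASAT number correct, and one Stroop score named before analysis. CW is one candidate. The choice belongs to the sponsor, since the only score section 6.4.1 commends is W+C. The paired t test already listed in section 9.4.3.1 serves for normally distributed changes.

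Label the other Stroop scores, RI, W+C and the Month 12 comparisons exploratory. State that none of them alone will be offered as support for the hypothesis in section 9.4.3.

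Do not make these comparisons conditional on the primary BICAMS result unless a single primary score and a success rule are defined first. Section 9.4.3.2 tests SDMT, CVLT2 and BVMTR with no such rule, so a gate could not be operated.

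Two named comparisons at 5% still leave some multiplicity. If independent, the chance of any significant result is 1 − 0.95² = 9.75%, and of a favourable one 1 − 0.975² = 4.9%. That is acceptable for secondary endpoints if stated.

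The cost is protocol and SAP wording, because every score is already collected. The small downside is that the remaining Stroop scores can only be reported descriptively.

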### **4.1 Inclusion criteria**

1. Diagnosed with RRMS as described in 2010 McDonald criteria (36)
2. Provided written informed consent prior to any intervention
3. Female or male patients aged 18-65 years
4. Unresponsive to treatment with a beta interferon or glatiramer acetate for a minimum of one year at and at adequate dose and with high disease activity

(Unresponsive patients: patients with no changes in relapses, increased relapses, severer relapses with one-year treatment or those who had had at least one relapse during the past one year under previous treatments and one or multiple contrast enhancing lesions in cranial MRI or increased T2 lesions in successive MRIs)

5. EDSS score below 5.5 at screening

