## **6.2 Patient demographics/other baseline characteristics**

Data of patient demographics and baseline characteristics will be collected from all patients that include: date of birth and sex. Relevant medical history/current medical condition data includes data until the start of study drug. If there is, concomitant diseases will be recorded. In addition, MS history and MS treatment will be recorded.

At screening, an ECG will be performed to ensure that the patients continue to meet inclusion criteria. Also an ECG will be performed prior to taking the first dose of fingolimod and after 6 hours of the first dose, the ECG will be repeated. Should any of the cardiac exclusion criteria is met based on the ECG results, the patient will not be allowed to participate in the study. ECGs will be printed out and will be kept at the study site as a source document.

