#### **9.6 Sample size calculation**

The primary objective of this study was set as investigating the effects of Fingolimod on cognitive performance in highly active relapsing remitting multiple sclerosis (RRMS) patients. Thus the primary end-point was planned as evaluating the effects of Fingolimod on cognitive performance in highly active, RRMS patients comparing cognitive performance at baseline and at Month 24, after treatment for two years as assessed by BICAMS battery test.

The Symbol Digit Modalities Test (SDMT) is one of the best known tests for detecting the cognitive impairment in patients with organic cerebral dysfunctions. The SDMT has a high sensitivity in detecting the presence of brain damage with providing data on cognitive functioning over time in response to treatment. The scoring of SDMT varies between 0-110 and in a study which evaluated age-related cognitive decline, baseline SDMT values for 50-64 years age group was 52.9 and for the 65+age group was 45.9 (34).

There are currently various clinical work is on-going for detection of decremental or incremental changes of cognitive function in RRMS patients and in a recent publication by Benedict et al which evaluated cognitive decline in RRMS patients, the mean SDMT score was found to be 53.1 for stable RRMS patients at baseline. In this study, the authors concluded that the increment of decline on SDMT was 3.5 raw score points, or roughly 6%. It was concluded that in overall, there seems to be an emerging consensus that a score change of 3-4 points on SDMT is clinically meaningful (35).

In this study, it is proposed to observe an increase of 3 points in SDMT testing (which roughly equals to 5% increase in SDMT overall score) is meaningful and in our study, with treatment

we may expect a 5% increase in cognitive functioning during a considerably longer duration of treatment and follow-up.

As per published literature, any cognitive improvement on the basis of SDMT test at a rate of % 5 should be evaluated as a significant improvement for RRMS patient with cognitive dysfunction. Thus, in this study we have postulated to reach a 5 % improvement in SDMT test at 24 months when compared to baseline in the cognitively impaired RRMS patients.

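### The cognition-MRI correlation in section 9.4.3.2 has no age adjustment; if levels are correlated, shared dependence on age can inflate it, while for 24-month changes the bias is small

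*Combined protocol and SAP*

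**What the plan says.** Section 9.4.3.2 (Secondary Objectives) gives the method: "Correlation between cognitive performance and MRI data will be calculated by using Pearson Correlation Coefficient (or Spearman Correlation Coefficient". The variables are those "between PASAT, STROOP and BICAMS tests scores and MRI parameters". Neither a visit nor a change score is named.

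Other sections describe the target differently. Section 2.3.2 lists the endpoint as the "correlation between effect of fingolimod on cognitive performances and brain atrophy (gray matter atrophy and thalamic atrophy) by comparing baseline and month 24", and section 9.4.2 says: "Correlation between effect of fingolimod on cognitive performances and brain atrophy will be explored". Section 2.2 also speaks of the effect of the drug. These three read as change from baseline.

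On age:
- Section 4.1 admits "Female or male patients aged 18-65 years".
- Section 6.2 says: "Data of patient demographics and baseline characteristics will be collected from all patients that include: date of birth and sex". Age is therefore available for every patient.
- Section 9.4.2 scales MRI volumes to head size or intracranial volume. It does not scale them to age.
- Sections 9.4.1 to 9.4.3 contain no partial correlation, regression or age-normed test score. Section 9.4.4 plans no supportive analysis.
- Section 9.6 cites, "in a study which evaluated age-related cognitive decline", the values "baseline SDMT values for 50-64 years age group was 52.9 and for the 65+age group was 45.9".

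**The concern.** Two quantities that each vary with age will correlate across patients of different ages, even if they are unrelated among patients of the same age. Scaling a volume to head size does not remove this. If test scores and brain volumes both fall with age, a crude coefficient mixes the association of interest with the spread of ages in the sample.

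The correlation is a listed secondary objective, and section 9.4.3.1 applies the two-sided 5% level to all analyses. A significant crude coefficient would probably be read as evidence that atrophy accompanies cognitive deficit in this disease. The plan as written offers no way to see how much of it reflects age.

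**Working it through.** **Number of patients.** The plan gives no figure for the correlation itself. Its sample size of 73 can be reproduced with a one-proportion precision formula: 1.96² × 0.05 × 0.95 / 0.05² = 72.99, so 73. The inputs p = 0.05 and half-width 0.05 are inferred, because section 9.6 gives no formula. It is not a correlation calculation. Enrolling 80 and losing 10% leaves 80 × 0.90 = 72, which is used below.

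**Critical value.** With n = 72 and t(70) = 1.994, the critical |r| = 1.994 / √(70 + 1.994²) = 0.232.

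**Correlation of levels.** If cognition and MRI have no link beyond age, the crude correlation equals r(age, cognition) × r(age, MRI). Two negative age correlations give a positive product. The chance of a two-sided significant result follows from Fisher's z with standard error 1/√(72 − 3) = 1/√69. The age correlations are assumptions. The last two columns come from simulation with linear age effects (20,000 replicates).

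| Assumed correlation of age with each | Induced r | Significant, Fisher z | Significant, crude (simulated) | Significant, age-partial (simulated) |
|---|---|---|---|---|
| 0.2 | 0.04 | 6.3% | 6.4% | 4.9% |
| 0.3 | 0.09 | 11.6% | 11.9% | 5.1% |
| 0.4 | 0.16 | 26.8% | 27.0% | 4.6% |
| 0.5 | 0.25 | 56.4% | 56.8% | 5.1% |

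The mean age-partial coefficient was 0.00 in each row.

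**What the section 9.6 figures can support.** The gap is 52.9 − 45.9 = 7.0 SDMT points. Take 57 as the middle of the younger group and 70 or 75 as the middle of the older one (assumptions). The slope is then 7/13 = 0.54 or 7/18 = 0.39 points per year. Converting this to a correlation needs an age SD and an SDMT SD, neither of which is in the documents: r = slope × SD(age) / SD(SDMT).
- With slope 0.39, age SD 10, SDMT SD 10 to 13 and an age-MRI correlation of 0.4, the induced r is 0.12 to 0.16 and the rejection rate 17% to 26%.
- With a shallower slope of 0.2, age SD 8 to 13.6, the same SDMT SDs and age-MRI correlations of 0.2 to 0.6, the induced r is 0.02 to 0.16 and the rejection rate 5% to 28%.

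**Correlation of 24-month changes.** If ageing is linear, two years shift every patient by the same amount, and a constant shift does not alter a correlation. Simulated rejection was 4.9%. If each change also correlates 0.2 with age, the induced r is 0.2 × 0.2 = 0.04 and rejection is 6.3%. At 0.3 each it would be 11.6%, but that requires the rate of change itself to depend on age to that degree.

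**The case against.** The strongest reply is that the objective concerns change. Sections 2.2, 2.3.2 and 9.4.2 all refer to the effect of treatment, and section 2.3.2 names baseline and month 24. On that reading age hardly matters. This stands, and it limits the point to correlations of levels. It does not dispose of it, because the only sentence an analyst would execute, in section 9.4.3.2, refers to scores and parameters.

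A reader might also infer that the protocol's own figures show SDMT falling across the enrolled age range. They do not. They compare ages 50-64 with 65 and over, so under an upper limit of 65 only patients aged exactly 65 fall in the older group. Nor is the cited sample described as having MS. The figures suggest that age matters to this test and no more. Setting the 7-point gap against the 3-point improvement sought would add nothing, since that improvement is a within-patient change for the primary endpoint.

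The age-MRI link is wholly assumed, because the documents give no relation between age and gray matter or thalamic volume. That is a fair limit on the size, and the range above starts near zero effect for this reason.

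Finally, the plan asks only for a correlation, to be explored. A crude coefficient does show that two measures vary together. It does not show that they do so at a given age. Exploratory status lowers the priority of the point but does not remove the ambiguity in interpretation.

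**Conclusion.** The concern holds in limited form. Section 9.4.3.2 plans a crude coefficient in a sample with a wide age range, and age is available but unused. If levels are correlated, age can inflate the coefficient. The false-positive rate for a link beyond age is about 6% to 56% when age correlates 0.2 to 0.5 with both variables at n = 72. These inputs are assumptions. If changes are correlated, the rate is about 5% to 6%, provided age correlates no more than about 0.2 with each change.

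A reader might conclude that ageing alone would produce a significant association. The documents do not support that. Of the four tabulated cases, only 0.5 with both variables gives an induced r (0.25) above the 0.232 threshold; in the others age adds to the coefficient without reliably making it significant. The point concerns one exploratory secondary analysis. It does not bear on the primary analysis or the sample size.

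**What to change.** Amend the correlation item in section 9.4.3.2 in two respects.

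1. State whether levels (and at which visit) or baseline-to-month-24 changes are correlated, and align the wording with sections 2.2, 2.3.2 and 9.4.2.
2. For any correlation of levels, make the main estimate a partial correlation adjusted for age at baseline (Pearson, or rank-based where Spearman would have been used), or a regression of the cognitive score on the MRI measure with age as covariate. Report the crude coefficient beside it.

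The analysis above supports adjustment for age only. Any further covariate, such as sex or the depression score, needs its own justification and should be named before the data are analysed.

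The cost is SAP wording and one degree of freedom (69 instead of 70 at n = 72). Date of birth is already collected, and no visit, assessment or patient is added.
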